#### 3.2. DLT Definition

Severity of adverse events will be graded according to CTCAE version 4.03 (see Appendix 2). For the purpose of dose escalation, any of the following adverse events occurring in the first two cycle of treatment (28 days) will be classified as DLTs, unless there is a clear alternative explanation (eg, related to underlying disease/progression):

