#### 5.4. Administration

## 5.4.1. Part A1 Monotherapy

PF-04518600 will be administered intravenously with adjustment for body weight at every cycle. A cycle is defined as the time from Day 1 dose to the next Day 1 dose. If there are no treatment delays, a cycle will be 2 weeks in duration. PF-04518600 will be administered on Day 1 of each 2 week cycle per the IP Manual as an intravenous (IV) infusion over 60 minutes (-5 to +15 minutes and should include the time needed to flush the infusion line) on an outpatient basis. If infusion reaction occurs, infusion rate maybe reduced (refer to Section 5.4.5.1 Infusion Reactions and Appendix 4 for management of infusion reactions).

The use of an infusion pump is the preferred method of administration to ensure accurate delivery of the investigational product, but gravity drips are allowed.

Each patient may receive PF-04518600 until disease progression by irRECIST (see Section 5.4.6 Treatment After Initial Evidence of Radiological Progression), patient refusal, or unacceptable toxicity occurs, or end of study, whichever occurs first.

The dose level will be assigned by the sponsor (Section 5.1 Allocation to Treatment). Patient actual body weight will be used to calculate the mg/kg dose, and the calculated dose will be rounded off to the second decimal point. All patients should be weighed within 72 hours prior to dosing for every cycle to ensure they did not experience either a weight loss or gain >10% from the prior weight used to calculate the amount of PF-04518600 required for dose preparation. Decision to recalculate PF-04518600 dose based on the weight obtained at each cycle can be in accordance with institutional practice, however if the patient experienced either a weight loss or gain >10% compared to the weight used to calculate the initial dose, the amount of PF-04518600 required for investigational product preparation and administration for the current cycle must be recalculated using this most recent weight obtained.

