# 5.4.2. Part A2 Monotherapy

PF-04518600 will be administered intravenously as a flat dose. A cycle is defined as the time from current Day 1 dose to the next Day 1 dose. If there are no treatment delays, a cycle will be 2 weeks in duration. PF-04518600 will be administered on Day 1 of each 2 week cycle per the IP Manual as an intravenous (IV) infusion over 60 minutes (-5 to +15 minutes and should include the time needed to flush the infusion line) on an outpatient basis. If infusion reaction occurs, infusion rate maybe reduced (refer to Section 5.4.5.1 Infusion Reactions and Appendix 4 for management of infusion reactions).

The use of an infusion pump is the preferred method of administration to ensure accurate delivery of the investigational product, but gravity drips are allowed. Please refer to the IP manual for infusion rate and duration.

Each patient may receive PF-04518600 until disease progression by irRECIST (see Section 5.4.6 Treatment After Initial Evidence of Radiological Progression), intolerability, death, or until end of study, whichever comes first.

The dose level will be assigned by the sponsor (Section 5.1 Allocation to Treatment).

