7.2.3. Safety Analyses

Safety data will be summarized using Pfizer standard data summary procedures.

Data will be summarized by cohort, defined by the initial dose. When the initial dose is determined to be the MTD, then the tables will also label the dose as the MTD.

A breakdown of demographic data will be provided for age, race, weight, body mass index, height, and tumor type by cohort defined by initial dose if data permits.

Adverse Events

Adverse Events (AEs) will be graded by the investigator according to the CTCAE version 4.03 and coded using the MedDRA. The focus of AE summaries will be on Treatment Emergent Adverse Events, those with initial onset or increasing in severity after the first dose of study medication. The number and percentage of patients who experienced any AE, serious AE (SAE), treatment related AE, and treatment related SAE will be summarized according to worst toxicity grades. The summaries will present AEs both on the entire study period and by cycle (Cycle 1 and Cycles beyond 1). The Safety Analysis Set will be used.

Laboratory Tests Abnormalities

The number and percentage of patients who experienced laboratory test abnormalities will be summarized according to worst toxicity grade observed for each laboratory test. The analyses will summarize laboratory tests both in the entire study period and by cycle (Cycle 1 and Cycles beyond 1). Shift tables will be provided to examine the distribution of laboratory abnormalities. The Safety Analysis Set will be used.

For laboratory tests without CTC grade definitions, results will be categorized as normal, abnormal high/low or not done.

Study Conduct and Patient Disposition

An accounting of the study patients will be tabulated. The subject evaluation groups will be listed. The Full Analysis Set will be used.

Subject discontinuation from treatment and study will be tabulated and listed separately with their reason for discontinuation. The Safety Analysis Set will be used.

Baseline Characteristics

Baseline characteristics such as demographics, prior medication, medical history, ECOG performance status, and primary diagnosis will be tabulated and listed. For ECOG performance status a shift table (worst post-baseline vs baseline may be produced). The Safety Analysis Set will be used.

Treatment Administration/Compliance

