Listings and tables by dose level will be provided. Cycle length is 14 days. Day 1 of a cycle is the first date of dose within that cycle. The safety analysis set will be used.

Dose modifications may occur in the following ways:

- Cycle delay—Day 1 of current cycle starts later than 14 days from Day 1 of the previous cycle (only applies to cycle 2 and above);
- Dose reduction—A decrease in the administered total daily dose (non-zero) compared to the planned total daily dose upon enrollment. If in the CRF the prescribed dose unit is mg/kg, but the actual dose is in mg the actual dose mg/kg should be calculated considering the body weight of the patient at that visit.

Intra-patient dose escalation is not allowed in this study. The following will be summarized by subject for each dose level:

- Number of subjects per dose level;
- Median and range of number of cycles started per subject;
- Number (%) of subjects starting a cycle (1, 2, 3...);
- Number (%) of subjects with cycle delays;
- Number (%) of dose interruptions (include both known and unknown dates);
- Number (%) of subjects with dose reductions;
- Number (%) of each reason (AE vs. Other) for cycle delays, dose interruptions and dose reductions;
- Time on treatment (median, range).

The following will be summarized by cycle received for each dose level:

- Total number of cycles started;
- Number of cycles started per subject (median, range);
- Number of cycles before 1st delay (median, range);
- Number of cycles before 1st reduction (median, range);
- Number of cycles before 1st interruption (median, range).

The following will be summarized for cumulative dose by dose level and cycle:

- Summary statistics (mean, median, standard deviation and range) of cumulative dose and percent of starting dose (compared to Day 1 dose of each cycle).

Listings by subject (ordered by dose level): start date and stop date of each dosing period within each cycle (including records with 0 mg), administered total daily dose for each period, any missed doses with unknown dates (Y/N), number of missed doses with unknown dates, reason for any dosing changes.

Listings by subject and each cycle (ordered by dose level): cycle length, total planned dose, administered total dose, percentage of planned dose, dose delay (yes/no), dose reduction (yes/no), and dose interruption (yes/no).

Prior, Concomitant, and Further Therapies

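### SAP 7.2.3 takes the percent of starting dose against the same cycle's Day 1 dose, which is 100% by construction for PF-04518600

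*SAP*

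**What the plan says.** The exposure part of SAP 7.2.3 fixes the time unit: "Cycle length is 14 days" and "Day 1 of a cycle is the first date of dose within that cycle". It then asks for the mean, median, standard deviation and range, by dose level and cycle, of cumulative dose and of "percent of starting dose (compared to Day 1 dose of each cycle".

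The protocol gives one PF-04518600 infusion per cycle. Section 5.4.1 (Part A1) states "PF-04518600 will be administered on Day 1 of each 2 week cycle" and adds "A cycle is defined as the time from Day 1 dose to the next Day 1 dose". Section 5.4.2 (Part A2) has the same schedule: "PF-04518600 will be administered on Day 1 of each 2 week cycle per the IP Manual". Sections 5.4.3 and 5.4.4 repeat it for Parts B1 and B2, and put utomilumab on Day 1 of every other cycle.

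Two other items in SAP 7.2.3 bear on the point:

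- A dose reduction is defined against the dose planned when the patient was enrolled, not against the current cycle's Day 1 dose.
- The percentage of planned dose appears only in a by-subject, by-cycle listing. No summary table reports it.

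**The concern.** A percent-of-starting-dose column should show how much of the assigned dose patients received. A within-cycle ratio can do that when a drug is taken daily, because doses may be missed or lowered between the first and last day of the cycle. With a single infusion on Day 1, nothing is given later in the cycle that could move the ratio.

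Protocol 5.4.5.6.1 allows Part A patients to be reduced by one dose level and, if needed, by two. The column would not register such a reduction. A reader of the study report could take a row of 100% values with no spread as evidence of full dose delivery, when it follows from the definition. Tolerability feeds into the choice of recommended phase 2 dose (Protocol 3.6, and the Part A2 primary objectives), so the table should not invite that misreading.

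**Working it through.** **Inputs**

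- Cycle length: 14 days (SAP 7.2.3).
- PF-04518600: one infusion per cycle, on Day 1 (Protocol 5.4.1 to 5.4.4).
- Utomilumab: Day 1 of cycles 1, 3, 5 and so on (Protocol 5.4.3 and 5.4.4).
- Dose levels: 0.01, 0.1, 0.3, 1.5, 3 and 10 mg/kg (Protocol 3.1.5.1, Table 2). The optional level between 3 and 10 is taken as not opened, in line with the six levels reported in Protocol 1.2.1.3.

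The plan states no figure for this column, so there is none to reproduce. The check applies the stated definition to the stated schedule.

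**Formula on the literal text**

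Percent in cycle k = 100 × (dose given in cycle k) / (Day 1 dose of cycle k). With one infusion per cycle, the dose given in cycle k is the Day 1 dose of cycle k, so the result is 100 for every k.

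**One-level reduction, PF-04518600**

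| Change (mg/kg) | Against same cycle's Day 1 dose | Against dose at enrollment |
|---|---|---|
| 10 to 3 | 3/3 = 100% | 3/10 = 30% |
| 3 to 1.5 | 1.5/1.5 = 100% | 1.5/3 = 50% |
| 1.5 to 0.3 | 0.3/0.3 = 100% | 0.3/1.5 = 20% |
| 0.3 to 0.1 | 0.1/0.1 = 100% | 0.1/0.3 = 33.3% |

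**Four-cycle course**

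Take a patient given 3, 3, 1.5 and 1.5 mg/kg. The amount delivered is 3 + 3 + 1.5 + 1.5 = 9 mg/kg, against 4 × 3 = 12 planned at enrollment, so 9/12 = 75%. The column shows 100% in all four cycles.

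**Utomilumab**

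At 20 mg the doses by cycle are 20, 0, 20, 0. The ratios are 20/20 = 100%, 0/0 (undefined), 100%, undefined.

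**Other readings of the parenthesis**

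- Numerator accumulated across cycles, same patient: 3/3 = 100%, 6/3 = 200%, 7.5/1.5 = 500%, 9/1.5 = 600%. This is not a usable percent.
- Denominator taken as the planned Day 1 dose of that cycle: an infusion stopped at 60% shows 60%. A reduced dose that is itself planned for that cycle still shows 100%.
- Each cycle's Day 1 dose compared with the patient's first dose: this gives the right-hand column of the table and is informative.

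The SAP does not say which reading is meant. Only the last one shows dose reductions as a sensible percent, and the wording does not state it.

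**The case against.** The strongest reply is that starting dose and initial dose elsewhere in the documents mean the patient's first dose. SAP 7.1 and 7.2.3, for example, define cohorts by initial dose. A programmer might therefore build the informative version. That is possible, but the parenthesis names the Day 1 dose of each cycle as the comparator, so the text needs correcting even if the intent was sound.

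A second reply is that the information is available elsewhere, and this largely stands. SAP 7.2.3 also tabulates:

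- cumulative dose;
- the number and percent of subjects with reductions, delays and interruptions, with reasons;
- cycles before the first of each;
- time on treatment.

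It also lists percentage of planned dose per subject and cycle. A reader might infer that the exposure tables cannot differ between the 30 mg and 250 mg arms of Part A2. The documents do not support that: cumulative dose in the same bullet will differ, and only the percent column is affected.

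A third reply is that Part B is hardly touched. Protocol 5.4.5.6.2 bars intrapatient reductions unless the combination level is judged above the MTD. That stands for PF-04518600 reductions. The undefined utomilumab ratio in even cycles remains.

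**Conclusion.** The point holds as a minor reporting defect. On the literal text, and with administered dose in both numerator and denominator, the column is 100% with zero spread for PF-04518600 at every dose level and cycle. For utomilumab, if the summary is applied to it, the ratio is undefined in every even cycle. The column also conflicts with the enrollment-dose reference that the same section uses for reductions. The consequence is confined to exposure reporting, mainly in Part A. The mTPI rules and the MTD estimate rest on DLT counts and do not use it.

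A reader might also infer that the split of adverse event and laboratory summaries is wrong, because SAP 7.2.3 states "The summaries will present AEs both on the entire study period and by cycle (Cycle 1 and Cycles beyond 1" while Protocol 3.2 refers to events "occurring in the first two cycle of treatment (28 days) will be classified as DLTs". Cycle 1 nominally covers 14/28 = 50% of that escalation window. The documents do not support calling this an error:

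- Cycle 2 events are correctly placed under later cycles.
- The primary DLT endpoint runs for 98 days (Protocol 2.2.1.1 and 2.2.2.1; SAP 2.3.1.1 and 2.3.2.1), so a 28-day cut would cover only 28/98 = 29% of it.
- DLTs are listed separately by dose level (SAP 7.2.1).
- SAP 5.9 promises adverse events by cycle.
- No decision depends on the Cycle 1 table.

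**What to change.** In SAP 7.2.3, replace the percent-of-starting-dose item with administered dose as a percent of the dose planned at enrollment, reported for each product, by cycle and cumulatively.

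- Parts A1 and B1, PF-04518600: use mg/kg, computed with the weight on which the dose was prepared. Protocol 5.4.1 does not require recalculation for weight changes of 10% or less, so another weight would create apparent departures from 100%.
- Parts A2 and B2, and utomilumab throughout: use flat mg.
- Utomilumab: include only cycles in which it is scheduled.

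This aligns the column with the section's own definition of a dose reduction and shows both reductions and incomplete infusions.

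The cost is a wording change and the reprogramming of one table. Planned and administered doses are already needed for the by-cycle listing, so no new data are required. An extra adverse event and laboratory summary for Cycles 1 and 2 together is optional and not part of the correction.

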- AST or ALT value ≥ 2 times the baseline values and $\geq 3 x$ ULN, or $\geq 8 x$ ULN (whichever is smaller).

For patients with pre-existing values of total bilirubin above the normal range:

- Total bilirubin level increased from baseline by an amount of at least $1 x$ ULN **or** if the value reaches $\geq 3 x$ ULN (whichever is smaller).

Graphs will be produced to examine the peak total bilirubin versus the peak ALT values, and the peak AST values (normalized to the ULRR of the respective lab parameter), respectively, in order to assess the potential DILI. In addition, individual subject line plots, mean (\pm SE) plots, mean change from baseline (\pm SE) plots by treatment over time may also be generated.

7.2.4. Other Safety Data – Screening and Other Special Purpose Data

Prior medication(s), non-drug treatment(s), medical history and physical examination will be listed in accordance with the sponsor reporting standards. Medical history will be mapped using the MedDRA thesaurus.

Urine Pregnancy test results will be presented in the listings.

Cardiac enzymes, troponin T and NT-pro BNP, and Hepatitis B, C and HIV tests results: hepatitis B surface antigen (HBsAg), hepatitis B core antibody (HBcAb), hepatitis C antibody (HCV Ab) and human immunodeficiency virus (HIV) serology will be listed. Summary tables of raw and change from baseline of HBV and HCV over time, and line plots of individual patients and group mean (\pm SE) will be generated by treatment group for monotherapy and combination therapy, respectively.

7.2.5. Pharmacokinetic Analyses

7.2.5.1. Pharmacokinetic Parameters

The PK parameters detailed in [Section 6.1](#) will be listed and summarized for subjects in the PK analysis set (as defined in [Section 5.4](#)). Missing values will be handled as detailed in [Section 7.1](#). Each PK parameter will be summarized by dose and cycle and will include the set of summary statistics as specified in the table below:

Parameter	Summary statistics
AUC _τ , AUC _{inf} , C _{max} , C _{min} , C _{av} , CL, V _{ss} , and R _{ac}	N, arithmetic mean, median, cv%, standard deviation, minimum, maximum, geometric mean and geometric cv%.
t _{1/2}	N, arithmetic mean, median, cv%, standard deviation, minimum, maximum

There will be 1 summary table presenting all PK parameters. This will include data from all cohorts and will be summarized by dose group and cycle.

To assess the relationship between the PK parameters (for each analyte) and dose, dose normalized AUC_τ and C_{max} will be plotted against dose (using a logarithmic scale), and will include individual subject values and the geometric means for each dose. Geometric means will have a different symbol than the individual values. The values will be dose normalized (to a 1 mg/kg dose) by dividing the individual values and raw geometric means by dose. A footnote will be added to the plots to indicate that geometric means are presented are presented on the plot.

7.2.5.2. Pharmacokinetic Concentrations

To assess the single dose PK profile of PF-04518600 PK concentrations will be listed, summarized and plotted for subjects in the PK analysis set (as defined in [Section 5.4](#)), where missing and BLQ values will be handled as detailed in [Section 7.1](#) above.

Presentations for PF-04518600 will include:

- A listing of all concentrations sorted by dose, subject ID, cycle, and nominal time post-dose. The listing of concentrations will include the actual sample collection times, and the time of dosing. Deviations from the nominal time will be given in a separate listing.
- A summary of concentrations by dose, cycle, and nominal time post-dose, where the set of statistics will include n, mean, median, standard deviation, coefficient of variation (cv), minimum, maximum and the number of concentrations above the lower limit of quantification.

- Median concentrations against nominal time post-dose by dose (based on the summary of concentrations by dose, cycle, and time post-dose), with all doses presented on the same plot. Two plots will be generated, so that the concentrations can be presented on linear and logarithmic scales.
- Mean concentrations against nominal time post-dose by dose (based on the summary of concentrations by dose, cycle, and time post-dose), with all doses presented on the same plot. Two plots will be generated, so that the concentrations can be presented on linear and logarithmic scales.
- Plots of individual concentrations against actual time post-dose (separate plots for each dose). Two plots per dose will be generated, so that the concentrations can be presented on linear and logarithmic scales.
- Plots of concentration against actual time post-dose by subject (separate line for each dose). Two plots per subject will be generated, so that the concentrations can be presented on linear and logarithmic scales.

For summary statistics and median plots by sampling time, the nominal PK sampling time will be used. For individual subject plots by time, the actual PK sampling time will be used.

CCI

7.2.7. Immunogenicity Analysis

Anti- PF-04518600 and Utomilumab antibody

A listing, sorted by subject and study day, of the result of anti- PF-04518600 and utomilumab antibody screening (positive/negative [<1 :negative]), the specificity, and titer will be listed. Summary counts of the patients, who are positive for the antibody, will be derived by study treatment and visit for the safety population. No summary statistics other than those cited above, will be generated.

Summary statistics and data listings of raw values and changes in immunophenotyping of circulating T cell subsets (naïve, effector, central memory and regulatory) and activation markers including, but not limiting to Ki67, and human leukocyte antigen (HLA)-DR at pre and post-treatment time points will be prepared.

9. APPENDICES

[This section is optional]

Appendix 1. DATA DERIVATION DETAILS

TBD

Appendix 1.1. Definition and use of visit windows in reporting

TBD

Appendix 1.2. Definition of Protocol Deviations that Relate to Statistical Analyses/Populations

TBD

Appendix 1.3. Further Definition of Endpoints

TBD

Appendix 1.4. List of Non-standard Listings, Figures and Tables Required

TBD
